6.1 General Approach

Intention-to treat. The primary analysis will follow the intention-to-treat (ITT) principle in order to evaluate the true outcome of the intervention as experienced by the patient who is blinded to the intervention.

Missing Data. It is anticipated that the data for some subjects will be incomplete for various reasons: missing daily-diary entries, refusal to answer a sensitive question on a questionnaire, onset of illness, loss-to-follow-up, etc. All occurrences of incomplete data will be investigated to carefully document the reasons for the missing data. If the primary outcome (amount of opioid used between 24 and 72 hours after surgery) cannot be ascertained with a reasonable degree of certainty, the patient will be excluded from the study.

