This material is the property of the NYU School of Medicine and Langone Medical Center. Do not disclose or use except as authorized in writing by the study sponsor

List of Abbreviations

ASA	American Society of Anesthesiologist Score
VAS	Visual analog scale
TSA	Total Shoulder Arthroplasty
ISB	Interscalene Nerve Block
DVT	Deep vein thrombosis
ER	Emergency room
AE	Adverse event
SAE	Serious adverse event
IV	Intravenous
PO	Taken orally
PRN	Taken as needed
TID	Taken three times per day
Q4h	Taken every four hours
CI	Confidence interval
SD	Standard deviation; a parameter, which characterizes a population distribution
SE	Standard error
ANOVA	Analysis of variance; a linear model
NSAID	Non-steroidal anti-inflammatory drug

CONFIDENTIAL

This material is the property of the NYU School of Medicine and Langone Medical Center. Do not disclose or use except as authorized in writing by the study sponsor
Interventional Template Version: 28 APR 2017

Protocol Summary

Title	Liposomal Bupivacaine (Exparel®) Plus 0.5% Bupivacaine HCL versus 0.5 % Bupivacaine HCL for Interscalene Nerve Block (ISB) for patients undergoing Total Shoulder Arthroplasty (TSA)
Short Title	Understanding the effects of Exparel® on post-operative pain management and opioid utilization for patients undergoing TSA
Brief Summary	This is a phase IV, randomized, single-blind, single-center study comparing patient related outcomes such as postoperative pain and opioid usage for patients who receive ISB's containing liposomal bupivacaine (Exparel®) plus 0.5% bupivacaine HCL versus 0.5% bupivacaine HCL undergoing total shoulder arthroplasty.
Phase	Clinical study phase IV
Objectives	To compare opioid utilization and pain management of patients who receive Exparel in an ISB vs standard 0.5% bupivacaine HCL during the initial 72-hour post-operative period. Additionally, to understand the duration of block after addition of Exparel® to bupivacaine in an Interscalene block after TSA
Methodology	phase IV, randomized, single-blind, single-center study
Endpoint	
Primary Endpoints: Opioid utilization expressed as (oral morphine mg equivalents) during the initial 72-hour post-operative period.
 
Secondary Endpoints: Duration of opioid use Patient reported pain scores (VAS) Length of stay Reported long-term narcotic use at home Documented opioid refills Adverse events such as respiratory depression, hypoventilation, reintubation, nausea, constipation

Study Duration	3 years
Participant Duration	Four weeks

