Duration of IP administration	Once during surgery
Population	184 participants scheduled for total shoulder arthroplasty (TSA)
Study Sites	NYU Langone Orthopedic Hospital
Number of participants	184
Description of Study Agent/Procedure	Injection of 20mL 0.5% Bupivacaine HCL versus 10mL Liposomal Bupivacaine plus 10mL Bupivacaine 0.5% in an Interscalene block for TSA
Reference Therapy	Reference is Bupivacaine 0.5% for Interscalene block
Key Procedures	Interscalene nerve block with Liposomal Bupivacaine + Bupivacaine 0.5%
Statistical Analysis	Intention-to-treat analysis will be performed with mean, t-tests, within and between group ANOVA and linear regression,

CONFIDENTIAL

This material is the property of the NYU School of Medicine and Langone Medical Center. Do not disclose or use except as authorized in writing by the study sponsor

1 Key Roles

Principal Investigator:

[name]

Assistant Professor of Anesthesiology
Department of Anesthesiology, Perioperative care and Pain Medicine
NYU Langone Orthopedic Hospital
NYU Langone Health
[name]
[name]
[contact]

Co-Investigators:

[name]

Professor of Anesthesiology
Department of Anesthesiology, Perioperative care and Pain Medicine
NYU Langone Orthopedic Hospital
NYU Langone Health
[name]
[name]

[name]

Assistant Professor of Orthopedic Surgery
Department of Orthopedic Surgery
NYU Langone Orthopedic Hospital
NYU Langone Health
[name]
[name]

2 Background and Specific Aims

With the growing elderly population, the number of total shoulder arthroplasty (TSA) surgeries is increasing. Nationwide, the total and partial shoulder replacements increased from about 18,000 in 2000 to over 45,000 in 2013 according to the American Academy of Orthopedic surgeons (AAOS). One of the greatest drivers of cost following TSA has been shown to be discharge disposition. Effective pain control after surgery is paramount because it facilitates rehabilitation and decreases hospital length of stay. Additionally, it may increase the likelihood of patients being discharged to their home rather than a rehabilitation or skilled nursing facility.

TSA is a procedure that is well confined within the dermatomal distribution of an interscalene brachial plexus nerve block (ISB), making it an ideal procedure to both evaluate and compare the regional potential of varying agents. Although the analgesic coverage is typically ideal, single shot injection of the long acting

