2.2 Objectives and Purpose

The goal of this study is to determine the effectiveness of Liposomal bupivacaine at reducing opioid consumption from 24-72 hours when used along with Bupivacaine 0.5% for single shot ISB for total shoulder arthroplasty. In addition, we would also like to determine if Liposomal bupivacaine is effective at prolonging the sensory block and reducing post-operative pain in patients after TSA surgery. We would also

CONFIDENTIAL

This material is the property of the NYU School of Medicine and Langone Medical Center. Do not disclose or use except as authorized in writing by the study sponsor

like to determine how reduction in post-operative pain impacts a patient’s hospital stay in the short term. Primary outcomes measures will be opioid utilization (in morphine milligram equivalents [MME]) during a 72-hour post-operative period. Secondary outcomes include patient reported pain scores, VAS. While it is expected that the greatest benefit of Liposomal bupivacaine plus Bupivacaine 0.5% will be seen within 24-72 hours after surgery, it is possible that there will be in an overall reduction in long-term opioid use (up to 4 weeks). Secondly, function/rehabilitation, length of stay, and complications may be impacted by combined use of Liposomal bupivacaine plus Bupivacaine 0.5%.

3 Study Design and Endpoints

ARM 1: Experimental	Sample Size: 92	10 mL Bupivacaine 0.5% + 10 mL Liposomal Bupivacaine
ARM 2: Control	Sample Size: 92	20 mL Bupivacaine 0.5%

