4.6 Total Number of Participants and Sites

Recruitment will end when approximately 184 participants are enrolled. It is expected that approximately 184 participants will be enrolled in order to produce 146 evaluable participants. The only site for enrollment will be the NYU Langone Orthopedic Hospital.

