6.2 Analysis of Endpoints

Primary Endpoints:

Opioid utilization (expressed as oral morphine mg equivalents) used during initial 24-72 hours post-operative period after surgery.

Secondary Endpoints:

CONFIDENTIAL

This material is the property of the NYU School of Medicine and Langone Medical Center. Do not disclose or use except as authorized in writing by the study sponsor

Duration of opioid use
Patient reported pain scores (VAS)
Length of stay
Progress with physical therapy
Reported long-term narcotic use at home
Discharge location: home, acute rehab or skilled nursing facility
Documented opioid refills
Adverse events such as respiratory depression, hypoventilation, reintubation, nausea, constipation

The analysis of opioid use, VAS, and PROMIS assessments will rely on a univariate analysis of variance model for mean score. This model is in the class of models commonly known as unirep-ANOVA models. It assumes that the mean score is a function of elapsed time and the treatment regimen assigned. This model considers the fact that the subject's repeated measures are correlated. The fitted model will provide statistical estimates of the mean levels, the treatment-effect differences between mean levels, the standard deviation, the intra-class correlation coefficient, 95% CIs, standard errors (SE), and statistical hypothesis tests. The estimates of means will be used to compute summary criteria such as area under the curve (AUC) for each regimen. All estimates reported will be presented their 95% CIs.

All endpoints will be evaluated as fits the data set with graphical figures such as scatter plots, box-and-whisker plots, and frequency histograms to visualize the distribution of these outcomes and their relationships to covariates and treatment assignment. When appropriate descriptive graphical and tabular methods will also be estimated and presented in a graphical figure.

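### Section 6.1 promises intention-to-treat but drops randomised patients whose opioid total is judged uncertain, by an undefined standard and with no missing-data method or sensitivity analysis

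*Combined protocol and SAP*

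**What the plan says.** On the analysis principle, Section 6.1 states: "The primary analysis will follow the intention-to-treat (ITT) principle". The Statistical Analysis row of the Protocol Summary agrees: "Intention-to-treat analysis will be performed with mean, t-tests, within and between group ANOVA and linear regression". Neither place defines ITT or an analysis set.

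On missing data, Section 6.1 expects incomplete records, including diary gaps and loss to follow-up, and asks that the reasons be investigated and documented. It then gives one handling rule: if the amount of opioid used between 24 and 72 hours "cannot be ascertained with a reasonable degree of certainty, the patient will be excluded from the study".

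On data sources, Section 3.1 has research staff visit inpatients to obtain and verify the medication taken. Patients discharged before 72 hours are given a diary and are telephoned. Attachment 14.3 also lets patients email the record. Section 3.1 blinds the staff who collect the data, and Section 8 requires missing case report form data to be explained.

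On expected loss, Section 4.6 says "approximately 184 participants will be enrolled in order to produce 146 evaluable participants". It does not define evaluable.

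**The concern.** Randomisation protects a comparison of everyone randomised. A rule that removes patients afterwards, according to whether their outcome record is good enough, gives up that protection unless the removals are unrelated to arm and outcome or are handled by a stated method. Here the standard is a matter of judgement. Two people applying it to the same diary could reach different answers, and the protocol does not say who decides, when, or whether blind to arm.

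The documents also contain a route by which ascertainability could depend on treatment. Inpatient use is verified by staff, while use after discharge rests on a diary and a call. Section 2.2 says that "length of stay, and complications may be impacted by combined use of Liposomal bupivacaine", and length of stay is a secondary endpoint. If the block changes when patients go home, it may change how many totals can be established in each arm.

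What is at stake is the primary comparison. It could be shifted in either direction, and no planned analysis would show whether that had happened.

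**Working it through.** **1. The plan's own figures.** Section 4.6: 184 − 146 = 38, and 38/184 = 20.7%. Section 3 gives 92 per arm. An assumed 20% loss reproduces the total: 73/0.80 = 91.25, rounded up to 92 per arm, or 184. That rate is inferred, not stated. The 146 cannot be reproduced, because Section 6.3 gives only the total and no alpha, power, effect or SD.

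**2. What the rule removes.** Totals that can be reconstructed from the hospital record, diary, call or email stay in. Totals that still fall short of the undefined standard go out. The repeated-measures ANOVA in Section 6.2 does not bring these patients back: it has no rule for incomplete records, and the exclusion takes effect before the model is fitted.

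**3. Bias formula.** Let p be the share excluded in an arm and g the retained-minus-excluded mean opioid use, in SD. The retained mean differs from the full-arm mean by p × g, so the bias in the difference between arms is p1·g1 − p2·g2. If p1 = p2 and g1 = g2, this is zero.

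**4. Illustration.** Assumptions that are not in the documents: two-sided 0.05, a two-sample t-test, half of the 38 falling under the rule (19, split 9 and 10), and the stated values of g.

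- Retained: 83 and 82. Average p = 19/184 = 0.1033. Standard error in SD units = √(1/83 + 1/82) = 0.1557.
- g differs between arms by 0.5 SD: bias = 0.1033 × 0.5 = 0.052 SD; noncentrality 0.052/0.1557 = 0.33; type I error 6.3%.
- g differs by 1.0 SD: bias = 0.103 SD; noncentrality 0.66; type I error 10.1%.

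Unequal exclusion with the same g in both arms gives similar values. With 14 against 5 excluded (78 and 87 retained), bias = (9/92) × g, which is 0.049 SD at g = 0.5 and 0.098 SD at g = 1.0. The type I error is 6.1% and 9.6%.

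**5. Scale.** With 83 and 82 retained, the difference detectable with 80% power (also assumed) is about 0.44 SD. Biases of 0.052 and 0.103 SD are about 12% and 24% of that.

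**6. The window.** The exclusion rule uses 24-72 h. The goal sentence of Section 2.2 agrees, and so does Section 6.2: "used during initial 24-72 hours post-operative period after surgery". The Protocol Summary has "during the initial 72-hour post-operative period", AIM 1 in Section 2.1 also uses the initial 72 hours, and Section 2.2 goes on to say "Primary outcomes measures will be opioid utilization (in morphine milligram equivalents [MME]) during a 72-hour post-operative period". This is a separate endpoint-definition conflict, but it leaves unclear which total must be ascertainable.

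**The case against.** The best defence has three parts.

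First, ITT is not defined in the protocol, and one common use of the term is simply analysis in the assigned arm. Nothing in Section 6.1 moves patients between arms, so the rule could be read as a complete-outcome restriction with a loose label. That is fair as to the label. It does not supply a threshold, a decider or a check on the restriction.

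Second, the safeguards are real. Data collectors and patients are blinded, the outcome has several sources, and reasons for gaps must be recorded. These make knowing selection unlikely and should keep the number excluded down. They do not restore balance if missingness itself is related to arm, and documented reasons are not an analysis.

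Third, the size is assumed throughout. That is correct. The figures show what could happen, not what will.

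Some stronger readings are tempting but not supported.

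- A reader might attribute all 38 non-evaluable patients to this rule. With a 1.0 SD difference in gaps, that would give a bias of 0.21 SD and a type I error of 23.6%. Section 4.6 gives no reasons for the loss, withdrawals may be part of it, and nothing in the documents supports gaps that large.
- A reader might conclude that the judgement will be unblinded, because Section 6.5 breaks the blind after a drug-related adverse event. That section mentions disclosure to the patient only and does not settle who else learns the assignment.
- A reader might take exclusion from the study to mean that secondary and safety data are discarded. Section 6.1 does not say either way.

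**Conclusion.** The point holds. As written, the primary analysis is a comparison of patients with ascertainable totals, selected after randomisation by an unstated standard and labelled ITT, with no planned check on the selection. That conclusion rests on the text alone.

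The harm is possible, not demonstrated, and its direction is unknown. Under the assumptions stated in the working, the illustrative range is a bias of 0.05 to 0.10 SD and a type I error of about 6% to 10%. With balanced exclusion and equal gaps only precision is lost. This should be fixed, because it concerns the primary analysis and the remedy is cheap. The documents do not show that the result will be biased.

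**What to change.** Replace the exclusion sentence in Section 6.1 with the following.

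1. All randomised patients are analysed in their assigned arm.
2. A complete total is defined objectively, for example every interval of the window covered by the hospital record, the diary or the call. Staff blind to arm make the judgement before database lock.
3. Incomplete totals are handled by a prespecified method. Multiple imputation using arm, in-hospital opioid use, pain scores and POD 7 opioid use is one example. A delta-adjusted or tipping-point sensitivity analysis accompanies it, and the ascertainable-only comparison is kept as supportive.
4. Incomplete totals and their reasons are reported by arm.
5. Secondary, safety and POD 7-30 data are retained for these patients.

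Separately, reconcile the primary window across the Protocol Summary, AIM 1 in Section 2.1, Section 2.2 (which uses both windows), Section 6.1 and Section 6.2, so that the rule refers to one endpoint.

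The cost is protocol and SAP wording plus modest analysis work. The data named above are already collected, so no extra patients, visits or calls are needed. Imputation rests on an assumption that cannot be tested, which is why the sensitivity analysis belongs in the fix.

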6.2 Analysis of Endpoints

Primary Endpoints:

Opioid utilization (expressed as oral morphine mg equivalents) used during initial 24-72 hours post-operative period after surgery.

Secondary Endpoints:

CONFIDENTIAL

This material is the property of the NYU School of Medicine and Langone Medical Center. Do not disclose or use except as authorized in writing by the study sponsor

Duration of opioid use
Patient reported pain scores (VAS)
Length of stay
Progress with physical therapy
Reported long-term narcotic use at home
Discharge location: home, acute rehab or skilled nursing facility
Documented opioid refills
Adverse events such as respiratory depression, hypoventilation, reintubation, nausea, constipation

The analysis of opioid use, VAS, and PROMIS assessments will rely on a univariate analysis of variance model for mean score. This model is in the class of models commonly known as unirep-ANOVA models. It assumes that the mean score is a function of elapsed time and the treatment regimen assigned. This model considers the fact that the subject's repeated measures are correlated. The fitted model will provide statistical estimates of the mean levels, the treatment-effect differences between mean levels, the standard deviation, the intra-class correlation coefficient, 95% CIs, standard errors (SE), and statistical hypothesis tests. The estimates of means will be used to compute summary criteria such as area under the curve (AUC) for each regimen. All estimates reported will be presented their 95% CIs.

All endpoints will be evaluated as fits the data set with graphical figures such as scatter plots, box-and-whisker plots, and frequency histograms to visualize the distribution of these outcomes and their relationships to covariates and treatment assignment. When appropriate descriptive graphical and tabular methods will also be estimated and presented in a graphical figure.

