
CONFIDENTIAL

This material is the property of the NYU School of Medicine and Langone Medical Center. Do not disclose or use except as authorized in writing by the study sponsor

local anesthetics, such as Bupivacaine, is limited in duration to the first postoperative day. Conversely, while interscalene perineural catheters offer the ability to continuously provide analgesia, they are time consuming to place, require daily maintenance, and often dislodge or migrate from the desired position. These limitations make interscalene perineural catheters problematic. In order to offer the longevity of an appropriately positioned catheter while preserving the simplicity of a single injection nerve blockade, this group proposes to evaluate the efficacy of liposomal bupivacaine or Exparel® in the setting of TSA.

Exparel® is a sterile, nonpyrogenic, preservative-free liposomal formulation of bupivacaine that provides a non-opioid option for postoperative pain control for up to 72 hours with single shot injection into the perineural space. The chemical and pharmacological nature of Exparel® allows for the encapsulated Bupivacaine to extend its duration of local anesthetic action by delaying medication release as compared to the injection of plain Bupivacaine. The FDA has recently approved Exparel® in its use for shoulder surgery via the interscalene nerve block. Exparel® has shown great potential with both its analgesic benefits and side effect profile; however, adequately powered trials are still necessary in order to compare its benefits to that of standard Bupivacaine.

To date, only one study has been published comparing bupivacaine alone to bupivacaine plus liposomal bupivacaine (1). In that study, the reduction in pain scores was minimal. However, there are several methodological issues with that study: 0.25% bupivacaine was used rather than 0.5%, resulting in a nerve block that was less dense, and making it mandatory to use general anesthesia; the study was probably underpowered; and analgesic use was not quantified.

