2.1 Specific Aims

AIM 1: To determine if Liposomal bupivacaine added to 0.5 % bupivacaine HCL in the interscalene nerve block during TSA surgery significantly changes post-operative opioid usage during the initial 72 hours post-operative period. This will be evaluated by randomizing patients to either receive 0.5% Bupivacaine HCL or Bupivacaine 0.5% with Liposomal bupivacaine in the interscalene nerve block. Opioid consumption will be evaluated in the immediate post-operative period, up to 72 hours post op and for up to 4 weeks after surgery.

AIM 2: To determine if the addition of Liposomal bupivacaine to Bupivacaine 0.5% in an interscalene nerve block prolongs post-operative nerve block and hence reduces post-operative pain from during the initial 72 hour post-operative period. Using the same groups as above, the patient stated duration of block (record time of onset of pain) and post-operative VAS Pain scores will be recorded in both the hospital and outpatient settings. Physical therapy endpoints will also be monitored and recorded.

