2.1 Statistical Hypotheses

We hypothesize that adding Liposomal bupivacaine to Bupivacaine 0.5% for the interscalene nerve block prior to TSA surgery will prolong the sensory block and reduce post-operative pain and opioid usage not only during the patients' inpatient hospital stay but also after discharge from the hospital for up to 72 hours. Furthermore, combining Liposomal bupivacaine and Bupivacaine will reduce complications associated with opioids such as constipation, nausea, pruritus, ileus and opioid dependency. Failing to reject the null hypothesis would signify that Exparel® has no clinically relevant impact on post-operative outcomes in TSA surgery as compared to plain Bupivacaine.

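### The primary endpoint has two different windows, the first 72 hours and 24-72 hours, and nothing in the plan says which governs

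*Combined protocol and SAP*

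**What the plan says.** Four statements carry the label primary, and they split two against two.

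**72 hours**
- Protocol Summary, Endpoint row: "Opioid utilization expressed as (oral morphine mg equivalents) during the initial 72-hour post-operative period".
- Section 2.2, outcome sentence: "Primary outcomes measures will be opioid utilization (in morphine milligram equivalents [MME]) during a 72-hour post-operative period".

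**24-72 hours**
- Section 6.1, Missing Data: "If the primary outcome (amount of opioid used between 24 and 72 hours after surgery) cannot be ascertained" with reasonable certainty, the patient is excluded.
- Section 6.2, Primary Endpoints: "Opioid utilization (expressed as oral morphine mg equivalents) used during initial 24-72 hours post-operative period after surgery".

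Other statements divide in the same way without using the label. Aim 1 asks whether the addition "significantly changes post-operative opioid usage during the initial 72 hours post-operative period". The goal sentence of 2.2 speaks of "reducing opioid consumption from 24-72 hours when used along with Bupivacaine 0.5"%, so section 2.2 uses both windows within one paragraph. The general hypothesis covers the inpatient stay "but also after discharge from the hospital for up to 72 hours".

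Section 6.3 states only that 184 subjects will be enrolled. Section 4.6 adds that this should yield 146 evaluable participants.

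**The concern.** The windows differ by the first 24 hours, and by the protocol's own account that period behaves differently from the rest. The Background says that a single injection of "local anesthetics, such as Bupivacaine, is limited in duration to the first postoperative day", and section 2.2 expects the greatest benefit between 24 and 72 hours. Adding or dropping the first day therefore changes the variable, its variance and the expected treatment difference.

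Three things follow.

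1. **The primary result depends on which section is read.** Section 6 leads to 24-72 hours; the Summary or the 2.2 outcome sentence leads to the 72-hour total. Either choice could be justified from the text after results are known. If both were tried and the better one reported, the nominal 5% error rate would not hold.
2. **The analysed population is affected.** The exclusion rule in 6.1 looks only at 24-72 hours. Under a 72-hour primary it would keep a patient whose first-day use is unknown.
3. **Timing matters.** Section 10.5 plans an interim safety and data analysis after 50 patients, by a board made up of the investigators. The window should be fixed before then.

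Time zero is also loose. Section 6 counts hours after surgery, which rules some readings out but does not choose between, for example, end of surgery and arrival in the recovery room.

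**Working it through.** **Step 1: compare the texts.**

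| Place | Window | Labelled primary? |
|---|---|---|
| Protocol Summary, Endpoint | first 72 h | yes |
| 2.1 Specific Aims, Aim 1 | first 72 h | no, an aim |
| 2.2, outcome sentence | 72 h | yes |
| 2.2, goal sentence | 24-72 h | no, a goal |
| 6.1, Missing Data | 24-72 h | yes |
| 6.2, Primary Endpoints | 24-72 h | yes |

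Dropping the two unlabelled rows leaves the conflict in place. The wording in 6.2 is itself mixed: initial suits a period that starts at zero, not one that starts at 24 hours.

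**Step 2: look for a sample-size basis that would settle it.** There is none. The stated N can be matched only as an attrition allowance: 146/2 = 73 per arm, and 73/(1 - 0.20) = 91.25, rounded up to 92 per arm, or 184, with 20% loss assumed. The loss implied by the stated figures is 1 - 146/184 = 20.7%. Neither figure points to a window.

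**Step 3: illustrate the consequence.** Every input except 73 per arm is an assumption.

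- Two-sample t test on window totals, two-sided 0.05, 73 per arm.
- 80% power on 24-72 h, which requires a standardized difference of d = 0.467 (noncentral t).
- The 24-72 h SD is set to 1. k = first-24-h SD divided by 24-72 h SD: 0.25, 0.5, 0.75, 1.
- r = correlation between the two periods: 0, 0.3, 0.5, 0.7.
- e = first-day benefit in first-day SDs.

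Formulas:
- SD72 = sqrt(1 + k² + 2rk)
- d72 = (0.467 + e·k)/SD72
- correlation of the two test statistics = (1 + r·k)/SD72
- first-day benefit at which both windows have equal power: e = 0.467·(SD72 - 1)/k

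*Power on the 72-hour total, extremes of the grid:*

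| e | k | r | SD72 | d72 | Power |
|---|---|---|---|---|---|
| 0 | 0.25 | 0 | 1.031 | 0.453 | 77.6% |
| 0 | 1 | 0.7 | 1.844 | 0.253 | 33.0% |
| 0.3 | 1 | 0.7 | 1.844 | 0.416 | 70.4% |
| 0.3 | 0.75 | 0 | 1.250 | 0.554 | 91.3% |

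*Equal-power first-day benefit:* from 0.467 × 0.0308/0.25 = 0.06 SD (k = 0.25, r = 0) to 0.467 × 0.844/1 = 0.39 SD (k = 1, r = 0.7). Below that value 24-72 h is the more powerful window; above it the 72-hour total is.

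*Type I error if both windows are tested at 0.05 and the better one is reported (bivariate normal, no effect in either period):*
- k = 0.25, r = 0.7: correlation 1.175/1.188 = 0.989, error 5.7%.
- k = 1, r = 0: correlation 1/1.414 = 0.707, error 8.3%.

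A simulation with t tests (40,000 runs) gave 5.8% and 8.3% at these two points.

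**The case against.** The strongest reply is that the text leans one way. Both relevant parts of Section 6 say 24-72 hours, and the 2.2 goal sentence, the timing of the research-staff visits in 3.1 and the expected period of benefit all fit it. An analyst would ordinarily follow the statistical section. That is convention, though. Nothing in the plan makes Section 6 override the Summary or 2.2, both of which call the 72-hour total primary. The ambiguity is reduced, not removed.

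The figures can also be challenged, and in part rightly.

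- Section 6.2 plans a repeated-measures ANOVA over time, whereas the calculation uses t tests on window totals. T-tests appear only in the Summary's list of methods.
- The grid caps the first-day SD at that of 24-72 h, with no support in the documents. Extending k to 2 takes the either-window error up to 9.2% (r = 0) and the no-effect power down to 17% (r = 0.7). The ranges are illustrations, not bounds.
- The plan does not propose testing both windows. The error figure shows what the ambiguity permits, not what is intended.
- Section 10.5 names no by-arm efficacy test and no opioid window for its interim analysis.

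First-day opioid use may well be available, since section 6.2.1 lists medications among the data held in the medical record. That is why confirmation of capture, and not a new procedure, is all that is asked for.

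None of these points touches the conflict in wording, which does not depend on the numbers.

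**Conclusion.** The concern holds and must be fixed. The Summary and the 2.2 outcome sentence name a 72-hour primary, sections 6.1 and 6.2 name a 24-72 hour primary, and no statement chooses between them. This is a contradiction in current text, not a missing detail. It leaves the confirmatory result undetermined, and the 6.1 exclusion rule fits only one of the two readings.

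Its numerical effect cannot be fixed from the documents. On the assumed grid, choosing the better window after testing both raises the type I error by 0.7 to 3.3 percentage points above 5%. Either window could be the more powerful, depending on how large any first-day benefit is. Confidence in the textual finding is high; the figures show only that the choice is not a formality.

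**What to change.** 1. State one primary window, with a defined time zero, in identical words in the Protocol Summary, Aim 1, 2.2, 6.1 and 6.2.
2. Make the 6.1 exclusion rule refer to that same window.
3. Name the other window as a secondary endpoint.
4. Do this before any by-arm data are seen, including at the analysis after 50 patients in section 10.5.

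The choice belongs to the sponsor. Taking 24-72 hours would agree with Section 6 and the 2.2 goal sentence; taking 72 hours would agree with the Summary, Aim 1 and the 2.2 outcome sentence. If the 72-hour total is chosen, confirm that first-24-hour opioid use is recorded and verified for every patient: Aim 1 intends to evaluate the immediate post-operative period, but section 3.1 describes in-hospital verification by research staff only for 24-72 hours.

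The cost is a wording amendment, plus that data check if the 72-hour total is chosen.
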